6.2.1.2 Dose-cohort Study Exploration and Stopping Rules

6.2.1.2.1 Dose Level Review Meetings

A Dose Level Review Team (DLRT) will review the safety data to evaluate DLT. The DLRT will be composed of the Investigator(s), Amgen Medical Monitor / Early Development Leader, Amgen Global Safety Officer or designee, Amgen Clinical Research Study Manager (CRSM) and Biostatistics representative or designee. Additional members may be added as needed (eg, clinical pharmacologist). A quorum, defined as \geq 50% of the participating investigators or their qualified designee (ie, sub-PI or research nurse or study coordinator possessing hard copy documentation [eg, e-mail]

of the PI's vote), must be in attendance for DLRM. The DLRM will be rescheduled if a quorum is not reached.

The DLRM members will recommend dosing decisions, which may include enrolling more subjects for DLT evaluation in part 1 of the study, de-escalation to a lower dose, delay or termination of dosing, or declare that the combination is tolerable based on DLT evaluation period data. All DLRT decisions will be communicated to team members via formal correspondence.

The Dose Level Review Team (DLRT) will evaluate data from all subjects enrolled into all cohorts including events with a longer onset time or events following exposure to multiple doses. If late onset events occur during a cohort, the DLRT may adaptively re-consider the doses evaluated within a cohort for subsequent dosing and/or possibly trigger a de-escalation or withholding of additional doses in subsequent cohorts. For Part 2 of the study, DLRT safety reviews will only be held during stage 1. A total of 3 DLRT safety reviews will occur: after the first 20 subjects (collectively from all 5 groups) have enrolled and completed 2 cycles of therapy, after an additional 20 subjects have enrolled and completed 2 cycles of therapy and after all subjects in stage 1 have enrolled completed 2 cycles of therapy.

The DLRT may request additional reviews or recommend modifying or suspending the study if safety concerns arise during the study. Refer to [Section 10.3.2](#) for additional details regarding the DLRT.

All DLRM requirements are outlined in the protocol. A DLRM Charter will not be used.

6.2.1.2.2 Rules for DLT Evaluation in Part 1 of the study

The DLT evaluation period for a subject is 21 days from the initial administration of study treatment. To be evaluable for a DLT, subjects must have had the opportunity to be on treatment for at least 21 days from the initial dosing of study treatment and have received at least 1 dose of AMG 820 and 1 dose of pembrolizumab in combination, or have a DLT during the DLT evaluation period after at least 1 dose of AMG 820 and pembrolizumab. Subjects may be replaced if they are not evaluable for DLT to obtain at least 6 DLT-evaluable subjects in a cohort during Study Part 1 (eg, a subject did not receive study treatment, or ended the study treatment before completion of DLT evaluation period for a reason other than experiencing a DLT).

Safety will be evaluated considering the incidence of DLTs among all DLT-evaluable subjects enrolled in part 1, which will include up to 3 cohorts. The initial cohort will treat subjects with 1400 mg AMG 820 plus 200 mg pembrolizumab Q3W using a 6+3 design.

- If 0 or 1 of the initial 6 evaluable subjects experience a dose-limiting toxicity (DLT) then the dose combination will be determined to be tolerable and Study Part 2 will be initiated.
- If 2 of the initial 6 evaluable subjects experience a DLT then 3 additional evaluable subjects will be enrolled.
- If 33% or more of the evaluable subjects experience a DLT then the dose combination will be determined to be non-tolerable and a second Part 1 cohort will be enrolled to test a decreased dose of AMG 820 in combination with 200 mg pembrolizumab. Further degree of dose modification and/or schedule of administration will be decided based on analysis of emerging safety and PK data.

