3.1.1 Phase 1b Study Design (Part 1)

Part 1 of the study has a single-arm 6+3 design aimed at assessing the safety of the selected starting dose of AMG 820 in combination with pembrolizumab. It will be conducted in subjects with select advanced solid tumors (CRC, pancreatic cancer, NSCLC and potentially other tumor types as per eligibility criteria). If the selected starting dose is determined not tolerable following review of safety data, additional lower dose levels will be evaluated. Up to 3 cohorts will be evaluated for safety and will include at least 6 subjects per cohort, and up to 18 subjects in total. The initial cohort will treat subjects at the selected starting dose of 1400 mg AMG 820 plus 200 mg pembrolizumab Q3W. The period for evaluation of a DLT in cycle 1 is 21 days. A

subject is not DLT-evaluable if he/she drops out before completion of cycle 1 for reasons other than an adverse event related to study drug.

- If 0 or 1 of the initial 6 evaluable subjects experience a dose-limiting toxicity (DLT) then the dose combination will be determined to be tolerable and Part 2 initiated.
- If 2 of the initial 6 evaluable subjects experience a DLT then 3 additional evaluable subjects will be enrolled.
- If 3 or more of the evaluable subjects experience a DLT (eg, 33% or higher with 9 evaluable subjects) then the dose combination will be determined to be non-tolerable and a second Part 1 cohort will be enrolled to test a decreased dose of AMG 820 in combination with 200 mg pembrolizumab. Further degree of dose modification and/or schedule of administration will be decided based on analysis of emerging safety and PK data.

Prior to opening a subsequent cohort for enrollment, the Dose Level Review Team (DLRT) will evaluate data from subjects enrolled into prior cohorts (at least 21 days of safety follow-up) including events with a longer onset time or events following exposure to multiple doses. If late onset events occur during a cohort, the DLRT may adaptively re-consider the doses evaluated within a cohort for subsequent dosing and/or possibly trigger a de-escalation or withholding of additional doses in subsequent cohorts.

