3.4 Replacement of Subjects

Subjects enrolled may be replaced if they are not evaluable for DLT (eg, a subject did not receive study treatment, or ended the study treatment before completion of DLT evaluation period for a reason other than experiencing a DLT).

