### **3.1.1 Phase 1b Study Design (Part 1)**

Part 1 of the study has a single-arm 6+3 design aimed at assessing the safety of the selected starting dose of AMG 820 in combination with pembrolizumab. It will be conducted in subjects with select advanced solid tumors (colorectal cancer [CRC], pancreatic cancer, non-small cell lung cancer [NSCLC] and potentially other tumor types as per eligibility criteria). If the selected starting dose is determined not tolerable following review of safety data, additional lower dose levels will be evaluated. Up to 3 cohorts will be evaluated for safety and will include at least 6 subjects per cohort, and up to 18 subjects in total. The initial cohort will treat subjects at the selected starting dose of 1400 mg AMG 820 plus 200 mg pembrolizumab Q3W. The period for evaluation of a DLT in cycle 1 is 21 days. A subject is not DLT-evaluable if he/she drops out before completion of cycle 1 for reasons other than an adverse event related to study drug.

- If 0 or 1 of the initial 6 evaluable subjects experience a dose-limiting toxicity (DLT) then the dose combination will be determined to be tolerable and Part 2 initiated.
- If 2 of the initial 6 evaluable subjects experience a DLT then 3 additional evaluable subjects will be enrolled.

- If 3 or more of the evaluable subjects experience a DLT (eg, 33% or higher with 9 evaluable subjects) then the dose combination will be determined to be non-tolerable and a second Part 1 cohort will be enrolled to test a decreased dose of AMG 820 in combination with 200 mg pembrolizumab. Further degree of dose modification and/or schedule of administration will be decided based on analysis of emerging safety and PK data.

Prior to opening a subsequent cohort for enrollment, the Dose Level Review Team (DLRT) will evaluate data from subjects enrolled into prior cohorts (at least 21 days of safety follow-up) including events with a longer onset time or events following exposure to multiple doses. If late onset events occur during a cohort, the DLRT may adaptively re-consider the doses evaluated within a cohort for subsequent dosing and/or possibly trigger a de-escalation or withholding of additional doses in subsequent cohorts.

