### **7.2 Dose Limiting Toxicity Analysis Set**

The Dose Limiting Toxicity Analysis Set will contain DLT-evaluable subjects (see protocol section 6.2.1.2.2 for definition of DLT-evaluable).

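### Read literally, protocol 6.2.1.2.2 leaves a DLT-level AMG 820 reaction out of the DLT count if it stops dosing before pembrolizumab; other clauses in the protocol and SAP point the other way

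*Protocol*

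**What the plan says.** Protocol 6.2 and 6.2.1.1 fix the order of dosing. AMG 820 goes first, over 60 minutes at the first dose, and pembrolizumab starts 15 minutes after it ends.

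Protocol 6.2.1.2.2 makes a subject DLT-evaluable by one of two routes. The first needs 21 days' opportunity on treatment, and the subject must "have received at least 1 dose of AMG 820 and 1 dose of pembrolizumab in combination". The second is "or have a DLT during the DLT evaluation period after at least 1 dose of AMG 820 and pembrolizumab". The same section adds: "Subjects may be replaced if they are not evaluable for DLT to obtain at least 6 DLT-evaluable subjects in a cohort". Its 6+3 cut-offs are stated on evaluable subjects, and protocol 10.1.2 restricts the DLT analysis to them.

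Protocol 3.1.1 has a different rule: a "subject is not DLT-evaluable if he/she drops out before completion of cycle 1 for reasons other than an adverse event related to study drug". SAP 3.1.1 repeats it (a subject who "drops out before completion of cycle 1 for reasons other than an adverse event related to study drug"), while SAP 7.2 points to the other rule: "The Dose Limiting Toxicity Analysis Set will contain DLT-evaluable subjects (see protocol section 6.2.1.2.2 for definition of DLT-evaluable".

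Protocol 3.4 says "Subjects enrolled may be replaced if they are not evaluable for DLT". The examples given there and in 6.2.1.2.2 are subjects who were not treated or who stopped early for some reason other than a DLT.

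**The concern.** A severe reaction in the first 75 minutes (60 + 15) can end dosing before any pembrolizumab is given. If it is grade 4, or is grade 3, does not clear within 6 hours and ends treatment as intolerable, it is on the toxicity list in 6.2.1.2.3, which covers events related to either drug. The protocol also directs the stop: 6.2.1.2.3 and 6.2.1.3 discontinue study treatment after a DLT. A site that follows those instructions leaves the subject without pembrolizumab, and so outside both evaluability routes.

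DLT is a primary endpoint, and the Part 1 count bears on whether Part 2 opens at 1400 mg or the AMG 820 dose is lowered. The events at risk of being lost are acute toxicities of AMG 820, the drug whose dose is under test, which about 25 people had received before this study (protocol 2.3).

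A grade 3 infusion reaction that settles to grade 1 or less within 6 hours is excluded from the DLT definition on purpose and is not part of this point.

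**Working it through.** **Clauses side by side**, for a subject with a related grade 4 AMG 820 reaction and no pembrolizumab:

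- 6.2.1.2.2, both evaluability routes: not evaluable.
- 10.1.2 and SAP 7.2: outside the DLT analysis set, because both follow 6.2.1.2.2.
- 6.2.1.2.3, start of the 21 days: both drugs given in combination, so the reaction precedes the period.
- 6.2.1.2.2, start of the 21 days: first study treatment, so the reaction is inside the period.
- 6.2.1.2.3, toxicity list: a DLT. The only infusion reaction carved out is the short-lived grade 3 one.
- 3.1.1 and SAP 3.1.1: evaluable. This follows by implication, since only drop-outs for other reasons are excluded.
- 3.4 and 6.2.1.2.2, replacement examples: not the kind of stop they describe.

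The first three leave the event out; the last four point to counting it.

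**The plan's own figure.** Protocol 10.2 gives a 47-91% chance of at least one DLT in 6 subjects at true rates of 10-33%. 1 − 0.90^6 = 0.469 and 1 − 0.67^6 = 0.910, so it reproduces.

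**Effect on one cohort.** Suppose the first six dosed include one such reaction and one other DLT. If counted: 2/6, so three more subjects are enrolled. If not counted: 1 of 5 evaluable, one replacement, and if the replacement has no DLT, 1/6, which is tolerable.

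**Effect on the chance of declaring the dose tolerable by the count.** Let d be the rate of other DLTs and a the rate of these reactions. Neither is in the documents; both are assumptions. With X ~ Bin(6, p):

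P(tolerable) = P(X ≤ 1) + P(X = 2) × (1 − p)^3

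Not counted (subject replaced): p = d. Counted: p = a + (1 − a)d.

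| d | Not counted | Counted, a = 2% | Counted, a = 5% | Counted, a = 11.3% |
|---|---|---|---|---|
| 10% | 95.7% | 93.5% (p = 0.118) | 89.4% (p = 0.145) | 77.7% (p = 0.202) |
| 20% | 78.1% | 74.4% (p = 0.216) | 68.4% (p = 0.240) | 55.6% (p = 0.290) |

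At a = 2% the shifts are 95.7 − 93.5 = 2.2 points and 78.1 − 74.4 = 3.7 points. The last column is a ceiling: 1 − 0.05^(1/25) = 0.113 is the one-sided 95% upper limit if none of the 25 first-in-human subjects had such a reaction. Protocol 2.2.1 names none among its key events but does not say there were none.

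**How often the worked cohort would arise.** Exactly one reaction and one other DLT among six has probability 30 × a × (1 − a)d × [(1 − a)(1 − d)]^4. With d = 10% this is 30 × 0.02 × 0.098 × 0.882^4 = 3.6% at a = 2%, and 30 × 0.05 × 0.095 × 0.855^4 = 7.6% at a = 5%.

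**The case against.** The best reply is that the second evaluability route and the start date in 6.2.1.2.3 are loose drafting, and that the other clauses show the event was meant to count. That is probably the intention. It does not settle the matter, because 10.1.2 and SAP 7.2 build the analysis set on 6.2.1.2.2, the section with the narrow wording.

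The second reply is that the count does not decide alone, and this stands. The review team evaluates data from all subjects enrolled (6.2.1.2.1), takes the cumulative adverse-event profile into account (6.2.1.2.3), reviews all available safety data before Part 2 opens (6.2.1.2.5) and must be unanimous (10.3.2). A reader might infer that Part 2 would open on 1/6 without anyone weighing the lost reaction; the documents do not support that. What the review does not do is put the subject back into the numerator or denominator.

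A reader might also infer that the same reaction counts if the site goes on to pembrolizumab and is lost if it stops, so that the worst reactions are the ones left out. That is not established. Under 6.2.1.2.3 the 21 days start at the combination, so a reaction before pembrolizumab could fall outside the period even if pembrolizumab followed. After a DLT, 6.2.1.2.3 and 6.2.1.3 already direct stopping, which leaves little to site choice.

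Finally, the practical reach is limited. The Amendment 2 rationale says the sponsor has decided to stop investigating the combination, and the SAP covers the final analysis. Nothing in the documents shows that such a subject existed, so it cannot be said that the DLT table is wrong.

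**Conclusion.** The rule is wrong as written, and the matter is minor. Literally applied, 6.2.1.2.2 leaves a DLT-level AMG 820 reaction that occurs before pembrolizumab out of a primary-endpoint count. It conflicts with 3.1.1, SAP 3.1.1, the replacement examples and its own start date.

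One such event can turn 2/6 into 1/6. The average effect depends on a reaction rate the documents do not give: 2 to 4 points at 2%, larger at higher assumed rates. The calculation assumes that the excluded subject is replaced, that subjects are independent, and that the count is applied mechanically. The last overstates the effect on actual dose decisions, because of the mandatory safety review.

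**What to change.** (a) Protocol 6.2.1.2.2, second route: replace the requirement for a dose of each drug with *after any amount of AMG 820 or pembrolizumab*.

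(b) Protocol 6.2.1.2.3: start the 21 days at the first administration of AMG 820 or pembrolizumab, to match 6.2.1.2.2. The DLT entry in SAP Section 6 also starts the period at the combination and should follow.

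(c) SAP 7.2: state this definition in full, and list any Part 1 subject who received AMG 820 but no pembrolizumab in cycle 1, with the reason. If Part 1 is complete, this step alone is operative.

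Leave the replacement wording in 3.4 as it is. Changing it to refer to related adverse events would open a new gap: a subject stopped by an excluded short-lived grade 3 reaction, with no pembrolizumab, would be non-evaluable yet outside the replacement example. Table 4 in 6.2.4.8 needs no change for this purpose; it covers pembrolizumab reactions, and how to manage AMG 820 reactions is a separate matter.

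The cost is a few words in the protocol, a definition and a short listing in the SAP, and no new procedures. Counting such an event could add three subjects to a cohort or contribute to a lower dose, which is what the 6+3 rule is for.

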Study Design: This is a multi-center Phase 1b/2 study testing the combination of AMG 820 and pembrolizumab in subjects with select advanced solid tumors. Phase 1b of the study (part 1) will have a 6+3 design aimed at assessing the safety of the selected starting dose of AMG 820 in combination with pembrolizumab. Phase 2 of the study (part 2) will further evaluate safety and test whether AMG 820 can enhance the anti-tumor activity observed historically with

pembrolizumab alone and/or overcome lack of response to pembrolizumab monotherapy in subjects with select solid tumors.

Part 1: Up to 3 cohorts will be evaluated for safety in Part 1. The initial cohort will treat subjects who have select advanced solid tumors with 1400 mg AMG 820 plus 200 mg pembrolizumab every three weeks (Q3W) using a 6+3 design.

- If 0 or 1 of the initial 6 evaluable subjects experience a dose-limiting toxicity (DLT) then the dose combination will be determined to be tolerable and Part 2 initiated. The study Part 1 DLT period is 21 days.
- If 2 of the initial 6 evaluable subjects experience a DLT then 3 additional evaluable subjects will be enrolled.
- If 3 or more of the evaluable subjects experience a DLT (eg, 33% or higher with 9 evaluable subjects) then the dose combination will be determined to be non-tolerable and a second Part 1 cohort will be enrolled to test a decreased dose of AMG 820 in combination with 200 mg pembrolizumab. Further degree of dose modification and/or schedule of administration will be decided based on analysis of emerging safety and PK data.

Part 2: The evaluation of safety and efficacy in this part will include 6-9 subjects from Part 1 who have been treated with the recommended combination dose, and will enroll additional subjects with select solid tumors up to 185 subjects overall. Part 2 will have 5 groups, which will be evaluated using a Simon two-stage design. Analysis of data in Part 2 will be done separately for each group (Group 1, 2, 3, 4a, 4b).

- Group 1 will enroll up to 43 advanced MMR-proficient CRC subjects who are naïve to anti-PD-1/PD-L1/CSF-1/CSF-1R therapies. Eighteen (18) subjects will be enrolled during the first stage and treated with the AMG 820 plus pembrolizumab combination. If only 2 or fewer subjects have an objective response per irRECIST then further enrollment may be discontinued; otherwise, enrollment up to 43 subjects will occur.

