3.1.2 Phase 2 Study Design

The primary objective of study Part 2 is to further evaluate safety and efficacy of the combination dose in the 4 selected CRC, pancreatic cancer and NSCLC subject groups. Other tumor types may be explored based on emerging data. The dose or doses to be evaluated in Part 2 will be based on results from Part 1. Part 2 will begin after safety of the dose level(s) explored in Part 1 has been assessed and determined to be safe.

Part 2 will include 6-9 subjects from Part 1 who have been treated with the recommended combination dose, and will enroll additional CRC, pancreatic cancer and NSCLC subjects following a Simon two-stage design: stage 1 will enroll up to 67 subjects overall, stage 2 may add another 118 subjects as per the rules described below. The recommendations to enroll stage 2 are based on ORR (see rules described below); nonetheless, the DLRT (see [Section 6.2.1.2.1](#)) will make decisions after reviewing all available safety, efficacy, pharmacokinetic and pharmacodynamic data. Analysis of data in Part 2 will be done separately for each group (Group 1, 2, 3, 4a, 4b).

- Group 1 will enroll up to 43 advanced MMR-proficient CRC subjects who are naïve to anti-PD-1/PD-L1/CSF-1/CSF-1R therapies. Eighteen (18) subjects will be enrolled during the first stage and treated with the AMG 820 plus pembrolizumab combination. If 2 or fewer subjects have an objective response per irRECIST then,

depending on the review of all available data, further enrollment may be discontinued; otherwise, enrollment up to 43 subjects will occur.

- Group 2 will enroll up to 29 advanced pancreatic cancer subjects who are naïve to anti-PD-1/PD-L1/CSF-1/CSF-1R therapies. Ten (10) subjects will be enrolled during the first stage and treated with the AMG 820 plus pembrolizumab combination. If no subjects have an objective response per irRECIST then, depending on the review of all available data, further enrollment may be discontinued; otherwise, enrollment up to 29 subjects will occur.

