6.2.1.2.5 Cohort Dose Level Determination

Study Part 1

A Dose Level Review Team (DLRT) will convene before a decision is made to open study Part 2. At the start of Part 1, enrollment of the first cohort of 6 to 9 evaluable patients will open for enrollment with a starting dose of AMG 820 1400 mg plus pembrolizumab 200 mg Q3W. Following subject completion of the DLT period, the DLRT will review all available safety data for the first cohort. If the data supports continued dosing at the selected starting dose, study Part 2 will be initiated at the same dose level. If it is determined that the starting dose is non-tolerable (if 33% or more of the evaluable subjects experience a DLT), dose de-escalation will occur and a second Part 1 cohort will be enrolled to test a decreased dose of AMG 820 in combination with 200 mg pembrolizumab Q3W. This will occur until identification of a well-tolerated dose for study Part 2. The AMG 820 (mg) pre-specified nominal cohort dose levels to be explored are 1100 mg and 800 mg Q3W. The pembrolizumab dose level will remain at 200 mg Q3W.

Part 2

Part 2 will have 4 groups, which will be evaluated using a Simon two-stage design:

Table 1. Study Part 2 Subject Groups

Naïve to anti-PD-1/PD-L1/CSF-1/CSF-1R treatment	
Group 1	CRC ^{MMR-proficient}
Group 2	Pancreatic Cancer
Group 3	NSCLC ^{PD-L1 low}
Refractory/ relapsing on anti-PD-1/PD-L1 + naïve to CSF-1/CSF-1R treatment	
Group 4a	NSCLC ^{PD-L1 low}
Group 4b	NSCLC ^{PD-L1 high}

The dose or doses (proposed recommended phase 2 dose, RP2D) to be evaluated in part 2 of the study will be based on results from part 1. The DLRT may determine the RP2D, which is defined as a dose(s) that is/are safe and produces pharmacodynamic effects. Emerging safety data may be used to re-challenge the selected dose in Study Part 1. If the initially selected dose is re-challenged, additional subjects may be enrolled in the corresponding cohort. In addition, the study may be discontinued or modified at any time due to documented safety findings.

Enrollment into the second stage of the Simon two-stage design will be determined by results through Study Part 2 stage 1.

All dose level and enrollment decisions will be formally communicated to investigators via a memorandum.

The dosing schedule is described by a [schema](#) in the protocol synopsis.

6.2.1.3 Dosage Adjustments, Delays, Rules for Withholding or Restarting, Permanent Discontinuation: AMG 820

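### The Part 1 rejection trigger of 33% or more has no denominator, so 2 DLTs in 6 meets both the expand and the reject rule; and the planned maxima of 18 and 197 do not fully allow for the +3 expansion

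*Protocol*

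**What the plan says.** **The DLT rule.** Protocol Section 6.2.1.2.2 accepts the dose at 0 or 1 DLT in the first 6 evaluable subjects. Its next bullet reads "If 2 of the initial 6 evaluable subjects experience a DLT then 3 additional evaluable subjects will be enrolled". The last reads "If 33% or more of the evaluable subjects experience a DLT then the dose combination will be determined to be non-tolerable". Section 6.2.1.2.5 repeats the percentage for a starting dose judged "non-tolerable (if 33% or more of the evaluable subjects experience a DLT), dose de-escalation will occur", with no separate expansion step beside it, although it describes the first cohort as having 6 to 9 evaluable patients.

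The synopsis, protocol Section 3.1.1 and SAP 3.1.1 word the rejection condition as a count: "If 3 or more of the evaluable subjects experience a DLT (eg, 33% or higher with 9 evaluable subjects". There the 33% is an example tied to 9 subjects.

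**The maxima.** Section 3.1.1 states: "Up to 3 cohorts will be evaluated for safety and will include at least 6 subjects per cohort, and up to 18 subjects in total". Sections 3.3 and 10.2 and SAP 3.2 give an overall range of 67 to 197, with at most 185 in Part 2.

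**Which cohorts may expand.** Section 3.1.1 attaches the design to the whole of Part 1: "Part 1 of the study has a single-arm 6+3 design". The synopsis and Section 6.2.1.2.2 attach it to the first cohort: "The initial cohort will treat subjects with 1400 mg AMG 820 plus 200 mg pembrolizumab Q3W using a 6+3 design". Section 3.1.2 adds: "Part 2 will include 6-9 subjects from Part 1 who have been treated with the recommended combination dose".

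**The concern.** Two of 6 is the outcome that the added 3 subjects exist to resolve. At exactly that outcome the section titled as the rules for DLT evaluation gives two instructions. The last bullet cannot be read as applying only after expansion, because it is the only bullet that covers 3 or more DLTs in the first 6. It must therefore operate at 6, where 2/6 also passes its threshold. Sections 6.2.1.2.1 and 10.3.2 say that no charter will be used for the dose review meetings, and Section 10.3.2 requires unanimous decisions, so the protocol text itself should have one reading.

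The maxima raise a separate problem. Three cohorts of at least 6 already fill 18 places, so a third cohort leaves no place for an expansion in any of them. The published counts then fall short of what the plan's own rule can require.

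**Working it through.** **Inputs.** Dose rules: Sections 3.1.1, 6.2.1.2.2 and 6.2.1.2.5. Counts: Sections 3.1.1, 3.1.2, 3.3 and 10.2. True DLT rates of 10%, 20% and 33% are assumptions within the 10-33% range that Section 10.2 uses. There are no replacements, and each expansion is completed to 9.

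**Plan's own figures reproduced.**
- P(at least one DLT in 6) = 1 - (1 - p)^6 = 46.9% at p = 0.10 and 91.0% at p = 0.33, matching the stated 47-91%.
- Part 2 maximum: 43 + 29 + 55 + 58 = 185.
- Part 1 maximum: 3 x 6 = 18.
- Overall maximum: 185 + 6 + 6 = 197, that is, two rejected cohorts of 6 outside the 185.

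**Overlap.** 2/6 = 33.3%, which is 33% or more. 3/9 = 33.3% rejects; 2/9 = 22.2% does not. The percentage and the count wordings therefore differ only at 2 of 6.

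**Effect of the literal reading.** With X ~ Binomial(6, p):
- Literal rejection: P(X >= 2).
- Intended rejection: P(X >= 3) + P(X = 2) x [1 - (1 - p)^3].

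| True DLT rate | P(X = 2) | Intended | Literal | Difference |
|---|---|---|---|---|
| 10% | 9.8% | 4.3% | 11.4% | 7.2 points |
| 20% | 24.6% | 21.9% | 34.5% | 12.6 points |
| 33% | 32.9% | 54.3% | 64.2% | 9.9 points |

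For example, at 20%: 0.0989 + 0.2458 x (1 - 0.512) = 0.2188.

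**Maxima under the +3 rule.** The cohort at the recommended dose, with its 6-9 subjects, counts inside the 185. Only rejected cohorts add to it.

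| Cohort sizes (third accepted) | Part 1 | Overall |
|---|---|---|
| 6, 6, 6 | 18 | 185 + 12 = 197 |
| 6, 6, 9 | 21 | 185 + 12 = 197 |
| 9, 6, 6 | 21 | 185 + 15 = 200 |
| 9, 9, 9 | 27 | 185 + 18 = 203 |

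So 18 excludes every expansion when there are three cohorts, while 197 excludes only expansion of a rejected cohort. With two cohorts, 9 + 9 = 18 fits.

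**How likely is Part 1 to exceed 18?** If every cohort may expand, it needs two rejections and at least one expansion: 0.2%, 4.1% and 22.9% at a common rate of 10%, 20% and 33%. If rates fall with dose, it is 2.1% (20/15/10%) and 9.1% (33/20/10%). If only the first cohort may expand and 2 of 6 rejects a later dose, the common-rate figures are 0.3%, 4.1% and 14.8%; if 2 of 6 does not reject a later dose, they are 0.04%, 1.2% and 7.2%.

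Exceeding 197 needs a rejected cohort that expanded and then a tolerated third dose. If every cohort may expand, that has probability 0.15%, 3.0% and 9.0% at the common rates. It also needs every Part 2 group to fill its second stage.

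**The case against.** The strongest reply is that the documents already settle the DLT rule. Three places state 3 or more and tie 33% to 9 subjects. Within Section 6.2.1.2.2, the specific bullet for 2 of 6 would have no effect if the general one overrode it. Section 6.2.1.2.5 itself describes a first cohort of 6 to 9, which presupposes expansion. This stands: the intended rule is recoverable. The 7 to 13 point differences therefore measure a misreading and are not the expected operating characteristics. A reader might infer that the trial has two rival safety rules with no way to choose between them; the documents do not support that. Any misreading would also drop a dose too readily; it would not keep a toxic one.

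On the maxima, the reply is that these are planning figures. The 197 is given as anticipated, Section 10.2 rests the Part 1 size on practical considerations, Section 6.2.1.2.1 lets the dose review team enrol more subjects for DLT evaluation, and Section 6.2.1.2.5 allows extra subjects on re-challenge. This also stands, so an inference that the trial would be blocked at 18 goes too far. A reader might equally infer that 197, like 18, rules out all expansion with three cohorts. It does not: 6 + 6 + 9 still gives 197.

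The larger probabilities come from a flat 33% DLT rate at 1400, 1100 and 800 mg. Nothing in the documents supports that rate. Section 2.2.1 reports a DLT in 1 of 25 subjects on AMG 820 alone, and the rate for the combination is unknown. Finally, the rationale for Amendment 2 records that the sponsor has decided to stop investigating the combination, so the remaining value of a correction is mainly an accurate record.

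None of this removes the textual conflict at 2 of 6 or makes 18 consistent with three cohorts under a 6+3 rule.

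**Conclusion.** The point holds as two drafting inconsistencies of minor severity; it does not challenge the 6+3 design.

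- The rejection trigger in Sections 6.2.1.2.2 and 6.2.1.2.5 is wrong as written at 2 of 6 and conflicts with the 3-or-more rule elsewhere. If it were applied literally, a dose would be rejected 7 to 13 percentage points more often at assumed DLT rates of 10-33%.
- The Part 1 maximum of 18 cannot accommodate any expansion across three cohorts. The overall 197 cannot accommodate expansion of a rejected cohort, but does cover expansion of the accepted one.
- The consistent maxima depend on which cohorts may expand: 27 and 203 if all may, 21 and 200 if only the first may. The first reading fits Section 3.1.1 and the 6-9 subjects expected at whichever dose is recommended. Neither reading gives 18 or 197. All four figures are before replacements and re-challenge enrolment.

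The textual conflict and the counts need no assumption about toxicity; only the probabilities do. No efficacy analysis, alpha or power is affected.

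**What to change.** 1. In Sections 6.2.1.2.2 and 6.2.1.2.5, replace the percentage condition with *3 or more DLTs among the initial 6 or the expanded 9 evaluable subjects*. This brings both into line with the synopsis, Section 3.1.1 and SAP 3.1.1.
2. State which Part 1 cohorts may expand. If all may, give the planned maxima as 27 evaluable subjects in Part 1 and 203 overall. If only the first may, give 21 and 200, and say how 2 of 6 is handled in a later cohort. In either case note that replacements and re-challenge enrolment are extra.
3. Carry the figures through the protocol synopsis, Sections 3.1.1, 3.3 and 10.2, and SAP 3.1.1 and 3.2.

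The cost is one phrase in two sections, a sentence or two on expansion, and two restated figures. The Part 2 design stays as it is.
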